7.1.2.4 Week 28 to End of Treatment (Every 4 weeks, ± 3 days)

- Laboratory tests (must be performed prior to next dosing cycle):
 - Week 28 followed by every 8 weeks: CBC with WBC differential
 - Week 28 followed by every visit where no CBC is collected: Hb only
 - Week 28 followed by every 8 weeks: Serum chemistry
 - Weeks 28, 36, 44, and 52 followed by every 12 weeks: Lipid panel (fasting whenever possible)
 - Week 28 followed by every 8 weeks: Serum iron, ferritin, TIBC, TSAT
 - Week 28 followed by every 8 weeks: CHr
 - Week 28 followed by every 16 weeks: HbA1c
 - Weeks 44, 68 and 84: Reticulocyte count
 - Weeks 44, 68 and 84: Special laboratory analytes (hepcidin, hsCRP)
 - Weeks 44, 68 and 84: Archival serum/plasma samples (optional donation, separate consent form)
- HemoCue assessment
- Week 36 followed by every 12 weeks: Targeted physical examination
 - Week 36 followed by every 12 weeks: Point of care qualitative urine pregnancy test for women of child bearing potential only
- Weeks 28, 52, and 76: 12-lead electrocardiogram
 - Dose adjustment review every 4 weeks (except/or more frequently in the event of excessive hematopoiesis). Refer to Section 2.1 and Appendix 1.
- All visit weeks: BP and B.
- All visit weeks: BP and heart rate
- Weeks 28, 52, and 76: HRQoL questionnaires (SF-36, FACT-An, and EQ-5D-5L)
- Adverse event recording
- Concomitant medication recording

- Procedures and nondrug therapy recording
- Dispense study drug (4 weeks supply), except at End of Treatment

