12.4 ADDITIONAL EFFICACY ANALYSES

The additional efficacy analyses will use the FAS population.

Additional efficacy analyses of continuous endpoints will use an MMRM model using baseline Hb and the parameter value as covariates and the other randomization stratification factors except baseline Hb (≤ 8 vs > 8), as fixed effects as outlined above. An ANCOVA model will be used for number of days hospitalized per PEY, rescue therapy used per PEY, etc. where MMRM model is not appropriate.

Additional analyses of proportions will use the CMH model adjusting for the randomization stratification factors. A CMH adjusted odds ratio and its associated 95% CI will be computed to compare between the roxadustat TIW group and pooled placebo. A two-sided 95% CI of the proportion based on the exact method of Clopper-Pearson will be computed for each treatment group.

Additional efficacy analyses of time-to-event endpoints will use the Cox Regression model. Median time to event and associated 95% CI will be estimated using Kaplan-Meier method.

Proportion of Hb values within 10.0-12.0 g/dL will be calculated in two ways:

Proportion of Hb values:

The following proportion in percentage for each subject will be defined:

*(Number of Hb values within 10.0-12.0 g/dL / Total number of protocol-planned Hb values) * 100* in weeks 28 to 36, 44 to 52 and 96 to 104 without use of rescue therapy within 6 weeks prior to and during this 8 week evaluation period. All scheduled and unscheduled hemoglobin

values that belong to each period will be taken into account using the analysis windows defined in Table 10.3-1.

Percentage of time:

[figure not shown]
The percentage of time each patient has Hb values within 10.0-12.0 g/dL will be calculated (as a percentage of the total of the length of time between the first and last Hb assessment during the evaluated period). The percentage of time will be calculated via linear interpolation. That is, if the change in Hb category (for instance from within 10.0-12.0 g/dL to > 12.0 g/dL) occurs between two visits V0 and V1, the day of change will be calculated by:

$$x = x_0 + (y - y_0) \frac{(x_1 - x_0)}{(y_1 - y_0)}$$

Where x_1 and x_0 are the dates when Hb was measured at V0 and V1 respectively, y_0 and y_1 are the Hb value at the respective visits V0 and V1 and y is the level of the Hb boundary (i.e. 12.0, 13.0 or 14.0g/dL).

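### SAP 12.4, Hb within 10.0-12.0 g/dL: the interpolation key reverses the visit dates, the boundary list omits 10.0, and the proportion lacks a clear counting rule

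*SAP*

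**What the plan says.** SAP 4.3 lists Hb within 10.0 to 12.0 g/dL among the additional efficacy evaluations, and SAP 12.4 defines two calculations.

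**Proportion of Hb values.** For each subject, the count of in-range values is divided by the "Total number of protocol-planned Hb values" and expressed as a percentage. The periods are Weeks 28-36, 44-52 and 96-104, with rescue therapy ruled out in the period and in the 6 weeks before it. The values that enter are described as "All scheduled and unscheduled hemoglobin" results falling in the period, and the windows are said to come from a Table 10.3-1.

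**Percentage of time.** Where Hb changes category between visits V0 and V1, the day of change is found by linear interpolation, x = x0 + (y − y0)(x1 − x0)/(y1 − y0). The key says that x1 and x0, in that order, "are the dates when Hb was measured at V0 and V1 respectively". It assigns y0 and y1 to the Hb at V0 and V1, and gives the boundary y as "i.e. 12.0, 13.0 or 14.0g/dL".

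Two general rules also bear on the proportion. SAP 5.4 groups unscheduled visits with the closest scheduled visit and uses the last measurement when a visit has several. SAP Appendix 1 (17.1) likewise takes the last non-missing value when two or more visits fall in one window.

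**The concern.** The date key and the Hb key disagree. The Hb values run V0 then V1 for subscripts 0 and 1, while the dates run the other way. A program written from the text would place each crossing at the wrong end of the interval.

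The boundary list does not fit the quantity being measured. A range of 10.0-12.0 has two limits; only the upper one is listed, with two levels that play no part in this range. The lower limit matters here: Protocol 5.1 requires a mean screening Hb of 10.0 g/dL or less, so a crossing of 10.0 is how a subject typically enters the range.

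In the proportion, numerator and denominator appear to count different things: every value obtained against only the values planned. If so, the result depends on how often a subject was tested and is not bounded by 100%.

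At stake is whether a pre-specified description of Hb control can be programmed in one way only.

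**Working it through.** The documents state no result for this endpoint, so there is no figure to reproduce. The Hb series below are illustrative assumptions, not trial data.

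**Date key.** Take Hb 11.5 on Day 0 (V0), 13.5 on Day 28 (V1) and boundary y = 12.0.
- Dates matched to the Hb subscripts (x0 = 0, x1 = 28): x = 0 + (12.0 − 11.5)(28 − 0)/(13.5 − 11.5) = Day 7. In range for 7/28 = 25% of the interval.
- Key as printed (x0 = 28, x1 = 0): x = 28 + (12.0 − 11.5)(0 − 28)/(13.5 − 11.5) = Day 21. In range for 21/28 = 75%.

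The error can go either way. For 11.0 to 12.5 over the same 28 days, the matched key gives 28 × 1.0/1.5 = Day 18.7 (66.7% in range) and the printed key gives 28 − 18.7 = Day 9.3 (33.3%). The two agree only when the crossing falls exactly at mid-interval, for example 11.0 to 13.0. A simple check shows the slip: with y = y0, the printed key returns the V1 date for the Hb measured at V0.

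**Boundary list.** Take Hb 9.5, 11.5 and 11.5 at Weeks 28, 32 and 36, a span of 56 days.
- With a 10.0 boundary, the crossing comes (10.0 − 9.5) × 28/(11.5 − 9.5) = 7 days after Week 28, so (56 − 7)/56 = 87.5% of the time is in range.
- The listed boundaries give no rule for that day. If no crossing were computed and all time at or below 12.0 counted as in range, the result would be 100%.

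**Proportion.** Protocol 7.1.2.4 schedules visits every 4 weeks from Week 28, with Hb taken from the CBC or as Hb only at each. Each 8-week period therefore has 3 planned values (for example Weeks 28, 32 and 36).
- All values counted: 3 scheduled plus 1 unscheduled, all in range, gives 4/3 = 133%; with 2 unscheduled, 5/3 = 167%.
- One value per window: the maximum is 3/3 = 100%.

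SAP 12.4 does not say which applies, and its table reference does not settle the matter: no Table 10.3-1 appears in the SAP text, and section 10.3 covers treatment compliance. The visit windows are in Table 17.1-1.

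**The case against.** The strongest reply concerns the proportion. SAP 5.4 says its guidelines cover all statistical analyses, and SAP 12.4 itself refers to analysis windows. On that reading, mentioning unscheduled values means only that such a value may fill a planned slot, and the ratio cannot pass 100%. This is a fair reading, so a result above 100% is conditional. It does not remove the ambiguity: SAP 12.4 speaks of all values, does not invoke the general rule, and departs from the last-value convention for percentage of time, where it averages same-day values.

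On the other two parts, the equation itself is right and ordinary program checking would probably expose the transposed key. A 10.0 boundary is also implied by the definition of the range, and the example figure is not available in the text reviewed. A reader might infer that the measure cannot detect a crossing of 10.0; that goes too far. What stands is that the printed key and list are wrong for this range.

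A reader might also infer that the planned-value denominator is an error because a missed visit counts as not in range: two in-range values and one missed visit give 2/3 = 67%. The documents do not support calling that a mistake. It can be a deliberate conservative choice, like the non-responder rule in SAP 4.1. An observed-only denominator would condition on retention, giving 100% to a subject with one in-range value followed by dropout. Percentage of time already uses only the span between the first and last observed Hb.

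Nor do the documents show that unscheduled Hb testing differs by arm. The differential dropout suspected in SAP 13.1.2 is raised about adverse event rates, and the study is double-blind.

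**Conclusion.** Two corrections are certain on the text: the date key is reversed, and the boundary list omits 10.0 while naming two levels outside the range. Read literally, the key mirrors every crossing within its interval; in the first example this moves time in range from 25% to 75%. The third part is a conflict between SAP 12.4 and the general rules in SAP 5.4 and Appendix 1. The proportion can exceed 100% if every value counts and cannot if one value per window counts. The sizes rest on the illustrative Hb series and on 3 planned values per period.

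The treatment of missed visits is a design choice. The measure is an additional endpoint outside the fixed-sequence testing described in SAP 5.3, so no primary or secondary conclusion, alpha or power depends on it.

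**What to change.** Amend SAP 12.4 as follows:

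1. Define x0 as the date of V0 and x1 as the date of V1.
2. List the boundaries for this range as 10.0 and 12.0 g/dL.
3. State that at most one Hb value per analysis window counts in the numerator, scheduled or unscheduled, consistent with SAP 5.4 and Appendix 1; or otherwise set one counting rule for both numerator and denominator.
4. Replace the reference to Table 10.3-1 with the windows of Table 17.1-1.

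The cost is a few lines of SAP wording and a check that the programs follow them. No new data are needed, and no other endpoint changes.

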13 SAFETY ANALYSES

The safety analysis will be performed using the Safety Population. Safety parameters include adverse and serious adverse events, laboratory parameters, vital signs, and ECG parameters. For each safety parameter, unless otherwise specified in section 5.4, the last assessment made prior to the first dose of double-blind study medication will be used as the baseline for all analyses.

13.1 ADVERSE EVENTS

Adverse events will be coded using MedDRA.

13.1.1 Proportion of Subjects with TEAE

An AE (classified by preferred term) occurring after the first dose of study medication and up to 28 days after the last dose of study medication will be considered a treatment emergent adverse event (TEAE) if it was not present prior to the first dose of study medication, or it was present prior to the first dose of study medication but increased in severity during the double-blind treatment period. An AE that occurs more than 28 days after the last dose of study medication will not be counted as a TEAE. TEAEs up to 3 days and 7 days after the last dose of study medication may also be evaluated.

The number and percentage of subjects reporting TEAEs in each treatment group will be tabulated by system organ class and preferred term; by system organ class, preferred term, and severity (≥ 3 in a separate table); and by system organ class, preferred term, and Investigator-determined relationship (at least possibly related in a separate table) to study medication. If more than one event occurs with the same preferred term for the same patient, the patient will be counted only once for that preferred term using the most severe and most related occurrence for the summarization by severity and by relationship to the study medication.

The distribution of TEAEs by severity and relationship to study medication will be summarized by treatment group.

The number and percentage of subjects reporting common ($\geq 5\%$ of subjects in any treatment group) TEAEs, treatment-emergent serious AEs (TESAE), renal TESAEs and AEs leading to discontinuation of study medication will be summarized by SOC, preferred term and treatment group, sorted in decreasing frequency overall. In addition, the number and percentage of death and fatal SAEs (i.e., events that caused death) will be summarized by treatment group, SOC and preferred term.

Sensitivity analysis of TEAE during study medication treatment will consist of a summary of TEAE and TESAEs reported after the first dose of study medication up until 72 hours (to cover > 4 half-lives of roxadustat post treatment) and 7 days after the last dose of study medication.

Treatment emergent major cardiovascular events (death, stroke, myocardial infarction) stratified by baseline eGFR (<10 , $10-<15$, $15-<30$, and ≥ 30 mL/min/1.73 m²) will be tabulated.

Listings will be presented of subjects with serious adverse events (SAEs), subjects with adverse events leading to discontinuation, and subjects who died.

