4 STUDY DESIGN

4.1 Description of the Study

This is a Phase 3, multicenter, randomized, double-blind, placebo-controlled study to evaluate the safety and efficacy of roxadustat in the treatment of anemic subjects with Stage 3, 4 or 5 CKD who are not on dialysis. This study is planned to recruit up to 1200 subjects from approximately 200 study centers worldwide.

This study will consist of three study periods as follows:

- Screening Period: Up to 6 weeks
- Treatment Period: Treatment duration is variable for individual subjects. In order to complete the Treatment Period simultaneously for all study subjects, the minimum treatment duration may be less than 52 weeks, with a maximum treatment duration of up to 3 years after the last subject is randomized.
- Post-treatment Follow-Up Period*: 4 weeks
(*or enroll into an Open Label Extension study)

Refer to Appendix 3 for a diagrammatic representation of the study schema.

Following the Screening Period, subjects will be randomized in a 2:1 ratio to receive roxadustat (approximately 800 subjects) or placebo (approximately 400 subjects). Dosing will be TIW throughout the study, except in subjects who have already converted to BIW or QW dosing regimens as a result of being enrolled under previous Study FGCL-4592-060 protocol versions. Starting doses of , respectively.

Table 1. Treatment Arms

Treatment Arms	Correction	Maintenance	n (FG-4592)	n (Placebo)
1A	TIW	QW	100 ^a	0
1P	TIW	QW	0	50 ^a
2A	TIW	BIW	100	0
2P	TIW	BIW	0	50
3A	TIW	TIW	100	0
3P	TIW	TIW	0	50

Abbreviations: A = active control; BIW = twice a week; n = number of subjects; P = placebo; TIW = three times a week; QW = once a week.

^a These numbers are based on a sample size of 450 and will increase if the overall sample size increases.

The initial study drug dose (per dose amount) is based on a tiered, weight-based dosing scheme shown in Table 2.

Table 2. Initial Study Drug (FG-4592 or Placebo) Dosing

Study Drug (Dose Frequency)	Low Weight (<70 kg)	Medium Weight (70 to 100 kg)	High Weight (>100 kg)
FG-4592/Placebo (TIW)	70 mg	100 mg	120 mg

Abbreviations: TIW = three times a week; QW = once a week.

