During the Treatment Period, subjects will attend consecutive weekly study visits for the first 2 weeks of study treatment (from Weeks 0 to 2) followed by every other week study visits starting at Week 4 until week 24. After Week 24, subjects will attend study visits every 4 weeks until the end of the Treatment Period. Treatment duration is variable for individual subjects. In order to complete the Treatment Period simultaneously for all study subjects, the minimum treatment duration may be less than 52 weeks, with a maximum treatment duration of up to 3 years after the last subject is randomized. After the Treatment Period, study subjects may enter a separate Open Label Extension study or will proceed to the 4-week post-treatment Follow-up Period, and will attend a final study visit at 4 weeks after end of treatment.

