10.3 Procedures for Eliciting, Recording, and Reporting Adverse Events

10.3.1 Adverse Event Reporting Period

The study period during which all AEs and SAEs must be reported begins after informed consent is obtained and ends 28 days after the last dose of study drug, except for pregnancy reporting (see Section 10.3.6). In addition, all AEs reported spontaneously by the subject to site personnel, outside the study period, may be recorded.

AEs will be followed until resolved, stable, or until the subject’s last study visit or lost to follow-up. If an AE is not resolved or stabilized at the subject’s last visit, it is up to the discretion of the Investigator and Sponsor’s Medical Monitor to determine if further monitoring of the event is warranted.

AEs collected prior to dosing of study drug will be considered “nontreatment emergent” while those reported after the first dose of study drug and up to 28 days after the last dose of study drug will be considered “treatment emergent” and be assessed for relationship to study drug.

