5.2.2 Safety Population

The Safety population will include all subjects who took any dose of study medication. All safety data will be analyzed using the safety population. If actual treatment received differs from the randomized treatment arm, the actual treatment arm will be used for analysis for the Safety population.

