10 STUDY MEDICATION

10.1 EXTENT OF EXPOSURE

Exposure to study medication will be summarized in terms of treatment duration, which is calculated as the number of days from the date of first double-blind medication taken to the date of last dose taken, inclusively.

Total weekly study drug exposure is defined as the total prescribed dose (in mg or mg/kg) of study drug administered within the week (per CRF dosing week).

Duration of exposure, weekly exposure and total study drug exposure will be tabulated by treatment group and overall for the safety population.

Per dose amount and dosing frequency for every four-week period will also be tabulated by treatment group for the Safety population.

Patient-Exposure-Year (PEY) is defined as $(\text{Last Dose Date} - \text{First Dose Date} + 1)/365.25$.

Patient-Followup-Year (PFY) is defined as $(\text{Last Dose Date} - \text{First Dose Date} + 28)/365.25$.

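### The 28-day TEAE window is not cut at entry to the open-label extension, so events on extension drug can be tabulated under the blinded arm

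*SAP*

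**What the plan says.** **Extension entry.** The Protocol offers the extension as an alternative to the post-treatment follow-up. Section 4.5.1 states: "After the Treatment Period, study subjects may enter a separate Open Label Extension study or will proceed to the 4-week post-treatment Follow-up Period". Section 4.1 attaches the same alternative to the follow-up period ("or enroll into an Open Label Extension study"), and the Synopsis agrees. The SAP never mentions the extension; its Section 3 lists only a 4-week follow-up.

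**TEAE window.** SAP 13.1.1 takes in AEs "occurring after the first dose of study medication and up to 28 days after the last dose of study medication" that were new or had worsened. Protocol 10.3.1 says that the AE reporting period "ends 28 days after the last dose of study drug, except for pregnancy reporting", and it treats AEs after the first dose and "up to 28 days after the last dose of study drug will be considered" treatment emergent. Protocol 9.4.4.1 starts from events in the double-blind treatment period but then excludes only those more than 28 days after the last dose.

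**Arm.** Under SAP 5.2.2, if the treatment received differs from the one randomized, "the actual treatment arm will be used for analysis for the Safety population". There is no rule for a later move into the extension.

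**Time.** In SAP 13.1.2, time at risk for a subject without the event runs to the last day of contact, which is not defined. SAP 10.1 defines follow-up years (PFY) with a fixed 28 days added for every subject.

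**Sensitivity summaries.** SAP 13.1.1 also plans TEAE and serious TEAE summaries to 72 hours and to 7 days after the last dose.

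**The concern.** A 28-day tail after the last dose makes sense if the subject is off drug in that time, because late events can then reasonably be laid to the blinded treatment. A subject who goes straight into the extension has no such period. For a former roxadustat subject who continues roxadustat, the event at least stays with the same drug. For a former placebo subject who starts roxadustat, an event under active drug would appear in the placebo column.

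Evaluating safety is a primary objective, and placebo is the comparator. Moving active-drug events into the placebo column works in one direction: it raises the placebo count and makes any excess on roxadustat look smaller. It matters most for events that occur soon after starting drug.

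**Working it through.** The plan states no figure on this point, so there is none to reproduce. The check is a reading of the rules, followed by an illustration of size.

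**1. Follow one subject through the rules.** Take a placebo subject whose last blinded dose is on day 0, whose first extension dose is on day 1, and who has a new AE on day 15.
- Reporting (Protocol 10.3.1): day 15 is within 28 days. The only stated exception is pregnancy, so the AE is reportable in this study.
- TEAE status (SAP 13.1.1): the AE follows the first dose and falls within 28 days of the last, so it is a TEAE.
- Arm (SAP 5.2.2): the treatment received in this study was placebo, so the AE goes in the placebo column.

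No step asks whether extension drug has started.

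**2. Look for a cut elsewhere.**
- SAP 12 ends the efficacy time-to-event period at last dose + 7 days or the EOT visit, whichever is first. This does not apply to TEAEs.
- SAP 13.1.2 censors selected TEAE summaries at chronic dialysis or transplant, not at extension entry.
- The opening of Protocol 9.4.4.1 could be read as excluding open-label time, but its 28-day sentence points the other way. It does not settle the matter.

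**3. Size of the exposed time.**

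Inputs: placebo subjects N = 150 (planned minimum) or 400 (planned maximum), from SAP 5.1; a 28-day tail, from SAP 13.1.1; the share f of placebo subjects rolling over directly, **assumed** at 30-70% because the documents give no figure; first extension dose **assumed** on the day after the last blinded dose.

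Patient-years = N × f × 28 / 365.25

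| N placebo | f = 30% | f = 70% |
|---|---|---|
| 150 | 150 × 0.3 × 28 / 365.25 = 3.4 | 150 × 0.7 × 28 / 365.25 = 8.0 |
| 400 | 400 × 0.3 × 28 / 365.25 = 9.2 | 400 × 0.7 × 28 / 365.25 = 21.5 |

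These are upper limits for each f. If the first extension dose comes g days after the last blinded dose, 29 − g days of the tail are on extension drug. At g = 15 that is 14 days, and each figure halves. At g above 28 there is no problem.

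**4. What the shorter windows leave.** 72 hours keeps 3 / 28 = 11% of the tail and removes 89%. Seven days keeps 7 / 28 = 25% and removes 75%.

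**The case against.** The strongest reply is that the documents do not establish the harmful sequence. The extension is a separate study. Neither document gives its drug, the gap before its first dose, or the database that records AEs after entry. If sites recorded those AEs only in the extension, they would not reach the placebo column; the tail would simply be unobserved for roll-over subjects. This stands as a limit on direction and size. It does not rescue the rule: Protocol 10.3.1 requires reporting to day 28 with no extension exception, so the text as written leads to the misattribution.

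The second reply is that the 72-hour and 7-day summaries would show a distortion when set beside the 28-day table. They do remove most of the tail. But they are sensitivity analyses, the main tables use 28 days, and neither is tied to extension entry.

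Three stronger readings are tempting and are not supported:
- **A stated percentage inflation of the placebo rate.** This would need a PFY-type denominator and an assumed rate ratio after starting drug. PFY is defined ("Patient-Followup-Year (PFY) is defined as") but no specified analysis uses it, and the documents give no rate ratio. The TEAE tables count a subject once per preferred term, and the exposure-adjusted rates in SAP 13.1.2 count subjects with a first event. A late event in someone already counted adds nothing.
- **A demonstrated error in the exposure-adjusted rates.** The last day of contact is undefined and could in practice be the EOT visit for extension entrants. Time at risk is therefore unspecified, not shown to be wrong.
- **Double counting of one event when studies are pooled.** That depends on the region-specific pooled SAP, which is not among these documents.

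**Conclusion.** The point holds in a limited form. The Protocol allows extension entry in place of the follow-up, and the main 28-day TEAE rule has no cut at that entry. Applied literally, it assigns events on extension drug to the blinded arm.

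The bias toward no difference rests on two assumptions: that the extension gives roxadustat and that it starts within 28 days. At 30-70% direct roll-over, itself assumed, the exposed placebo time is at most about 3-8 patient-years with 150 placebo subjects, or 9-21 with 400. That is small beside a treatment period that may last well over a year, and the shorter-window summaries give partial protection. The change is worth making because the rule is ambiguous at best and the correction is cheap. Nothing here suggests that the safety comparison as a whole is unreliable.

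**What to change.** - **SAP 13.1.1, with matching wording in Protocol 9.4.4.1:** end the TEAE window at the earlier of last blinded dose + 28 days and the day before the first extension dose.
- **SAP 13.1.2:** define last day of contact so that time at risk ends no later than that same date.
- **Listing:** show events from the first extension dose to day 28 separately by blinded arm, so that nothing is lost from view.
- **Data:** bring the first extension dose date into the analysis dataset.
- **Optional:** align PFY in SAP 10.1 for consistency.

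The cost is one derived date and a few sentences. No visit, assessment or treatment changes. The downside is slightly shorter post-dose follow-up for roll-over subjects, so a late effect of blinded treatment that emerges after extension entry would appear only in the separate listing.
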